9.2.5 Adverse Events

Adverse events, whether in response to a query, observed by site personnel, or reported spontaneously by the subject will be recorded. Adverse events definition and serious adverse event categories are described in detail in Section 11.0.

9.3 Variables

Variables:

Primary Variable

- Change in HAQ DI score at weeks 12 and weeks 24 weeks from the baseline

Secondary Variable

- Change in other PROs (SF-36 domain scales, EQ-5D Index, Work Productivity and Activity Impairment Questionnaire [WPAI]) from baseline to weeks 12 and 24
- Change in patient satisfaction questions from baseline to weeks 12 and 24
- Number and percent of patients achieving a clinically meaningful improvement on the HAQ DI, from baseline to weeks 12 and 24
- Healthcare Resource Utilization (HCRU) at baseline, 12 and 24 weeks

Additional Secondary Variable

- Change in HAQ DI score from baseline to 24 weeks
- Changes in the disease severity and PROs from baseline to 24 weeks

9.4 Data Sources

Case Report Forms (CRFs) and patient questionnaires.

Collection of data includes but not limited to subject demographics, clinical history, comorbidities, spontaneous adverse events, and concomitant medications. The following questionnaires will be utilized to collect data directly from participating subjects:

- EQ-5D
- SF-36
- HAQ DI
- WPAI
- HCRU
- Patient Global Impression of Change (PGIC)
- Patient Treatment Satisfaction Questions

9.5 Study Size

Approximately 89 patients diagnosed with RA will be recruited. The sample size was calculated by assuming an alpha of 0.05 and a power of 0.80 in a one-sided test, $Z(1-\alpha) = 1.645$ and $Z(1-\beta) = 0.842$. As to the primary variable, assuming a mean Δ HAQ-DI of -0.21 and a standard deviation (SD) of 0.5, according to the formula, 36 subjects are required. Then, given the importance of the secondary endpoint (WPAI), an improvement of 9.9 ± 25 hours of work time lost (mean=9.9, SD=25) requires 40 subjects. However, we assume a 50% employment rate in the study population and a drop-out rate of 10%, eventually approximately 89 patients will be required ($40/0.5/(1-0.1) = 89$).

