
2. Participation in any RA-related clinical trial at the time of enrolment, at baseline or at any point during the past 24 weeks prior to baseline3. Patients, who in the clinician's view, may not be able to accurately report their QoL or prior resource utilization4. Patients, who in the clinician's view, may not be able to adhere to adalimumab therapy over 24 weeks.
--

Variables:**Primary Variable**

- Change in HAQ DI score at weeks 12 and weeks 24 weeks from the baseline

Secondary Variable

- Change in other PROs (SF-36 domain scales, EQ-5D Index, Work Productivity and Activity Impairment Questionnaire [WPAI]) from baseline to weeks 12 and 24
- Number and percent of patients achieving a clinically meaningful improvement on the HAQ DI, from baseline to weeks 12 and 24
- Healthcare Resource Utilization (HCRU) at baseline, 12 and 24 weeks

Additional Secondary Variable

- Change in HAQ DI score from baseline to 24 weeks
- Changes in the disease severity and PROs from baseline to 24 weeks

Exploratory Variable

- Change in patient satisfaction questions from baseline to weeks 12 and 24

Data Sources: Case Report Forms (CRFs) and patient questionnaires. Collection of data includes but not limited to subject demographics, clinical history, comorbidities, spontaneous adverse events, and concomitant medications. The following questionnaires will be utilized to collect data directly from participating subjects:

- EQ-5D
- SF-36
- HAQ DI
- WPAI
- HCRU
- Patient Global Impression of Change (PGIC)
- Patient Treatment Satisfaction Questions

Study Size: Approximately 89 patients diagnosed with RA that meet the inclusion and exclusion criteria will be enrolled at approximately 9 sites in Korea. The sample size was calculated by assuming an alpha of 0.05 and a power of 0.80 in a one-sided test,

resulting in 36 subjects required to recognize a statistically significant improvement in HAQ DI (-0.21). Then, given the importance of other secondary endpoints, an improvement of 9.9 ± 25 hours of work time lost requires 40 subjects. However, since it is expected that approximately half the study population may no longer be working due to their age, we assume a 50% employment rate in the study population and a drop-out rate of 10%, eventually approximately 89 patients will be required to achieve the required number of respondents.

Data Analysis:

Primary Endpoint Analysis

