The WPAI is a patient-reported questionnaire to measure work and activity impairment during the past seven days. It determines employment status, hours missed from work due to the disease (i.e. RA), hours missed from work for other reasons, hours actually worked, the degree to which the disease affected work productivity while at work and the degree to which the disease affected activities outside of work. Additional questions around employment status will be incorporated into the survey. The completion time for the WPAI is approximately 2-5 minutes. The full version of WPAI is presented in Appendix G.

Patient Global Impression of Change (PGIC)

The PGIC measures the patient's perceptions of changes in their disease. It consists of one question asking about the change in their condition; for this study, the base will be "since you initiated your adalimumab treatment". The completion time for the PGIC is less than 1 minute. The full version of PGIC is presented in Appendix H.

Patient Treatment Satisfaction Questions

The patient treatment satisfaction questions were developed de novo for this study and are not considered "validated" questions. Self-administered by the patient, the completion time for the patient treatment satisfaction questions is approximately 1-2 minutes. The full version of patient treatment satisfaction questions are presented in Appendix I.

Healthcare Resource Utilization (HCRU) Questionnaire

The HCRU questionnaire will collect data on the healthcare resources consumed in the prior 3 months, as recall beyond 3 months may be problematic in an older population(16). HCRU collection will include data such as the number of physician visits and to which physician (GP, specialist), Emergency Department visits, hospitalizations, and other drugs

as well as devices and aids purchased to assist in their mobility due to RA. The HCRU questionnaire will be part of the patient questionnaire and will be distributed to patients together with the PRO questionnaires (Appendix D to Appendix I). The full HCRU questionnaire is presented in Appendix J.

All of the questionnaires will use the validated Korean version.

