9.7.2 Analyzable population

All subjects who received at least one dose of adalimumab during the study will be included. The main analysis will be conducted on the pooled population, where appropriate, with each individual country analyzed separately as supportive data.

9.7.3**Planned Methods of Statistical Analysis**

All statistical tests will be two-tailed with a significance level of 0.05. Descriptive statistics will be provided. Descriptive analysis will be conducted on all key parameters and presented as mean, standard deviation, minimum, maximum, and median when continuous and as “n” and percent when categorical. Change from adalimumab initiation to 24 weeks will be calculated and evaluated for significant improvements using paired t-tests / ANOVA for parametric and Wilcoxon signed-rank for non-parametric data. Analysis will be also be conducted by severity level (moderate vs severe), disease duration quartile (to compare to prior work) and up to two (2) other subgroups. Cochran-Armitage test of trends or other similar methods may be used to compare categories of subjects.

9.7.4**Primary Endpoint Analysis**

The primary endpoint variable will be the change in HAQ DI score at 24 weeks after the initiation of adalimumab (observed population).

The objective of the primary endpoint analysis will be to demonstrate that treatment with adalimumab improves functioning as measured by the HAQ DI in subjects with RA following treatment initiation. This change will be summarized as the mean and 95% confidence interval and will be tested with a paired t-test.

The primary analysis will be summarized as the mean and 95% confidence interval and will be tested with a paired t-test without adjusting for baseline disease severity. For sensitivity analysis, the mean change in HAQ DI at Week 24 will be analyzed using ANOVA adjusting for baseline disease severity.

9.7.5**Secondary Endpoint Analysis**

The main secondary endpoint variable will be the change in HAQ DI at 12 weeks after the initiation of adalimumab.

The objective of endpoint analysis will be to demonstrate that treatment with adalimumab improves functioning as measured by HAQ DI in subjects with RA compared to baseline.

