The main secondary analysis will be summarized as the mean and 95% confidence interval and will be tested with a paired t-test without adjusting for baseline disease severity. For sensitivity analysis, the mean change in HAQ DI at Week 12 will be analyzed using ANOVA adjusting for baseline disease severity.

Other secondary analysis include:

- Change in other patient reported outcomes (SF-36 domain scales, EQ-5D Index, WPAI total lost productivity) at weeks 12 and 24 after the initiation of adalimumab, in those patients continuing on adalimumab (observed population). These changes will be summarized as the means and 95% confidence intervals and will be tested with paired t-tests.
- Number and percent of patients achieving a clinically meaningful improvement on the HAQ DI, as defined by a -0.22 point improvement or greater, at weeks 12 and 24 after the initiation of adalimumab (observed population).

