Appendix G. Work Productivity and Activity Impairment (WPAI)

Work Productivity and Activity Impairment Questionnaire: Rheumatoid arthritis V2.0 (WPAI:RA)

The following questions ask about the effect of your rheumatoid arthritis on your ability to work and perform normal daily activities. *Please fill in the blanks or circle a number, as indicated.*

1. Please check your current employment status.

 1	Full time (working for pay)
 2	Part time (working for pay)
 3	Volunteering
 4	Stopped working because of my RA
 5	Stopped working for other reasons
 6	Retired

*If your response is 1 or 2, continue the survey.
If your response is 3-6, skip to question 6.*

The next questions refer to the **past seven days**, not including today.

2. During the past seven days, how many hours did you miss from work because of problems associated with your rheumatoid arthritis? *Include hours you missed on sick days, times you went in late, left early, etc., because of your rheumatoid arthritis. Do not include time you missed to participate in this study.*

_____ HOURS

3. During the past seven days, how many hours did you miss from work because of any other reason, such as annual leave, holidays, time off to participate in this study?

_____ HOURS

[figure not shown]
4. During the past seven days, how many hours did you actually work?

_____ HOURS (If "0", skip to question 6.)

5. During the past seven days, how much did your rheumatoid arthritis affect your productivity while you were working?

Think about days you were limited in the amount or kind of work you could do, days you accomplished less than you would like, or days you could not do your work as carefully as usual. If rheumatoid arthritis affected your work only a little, choose a low number. Choose a high number if rheumatoid arthritis affected your work a great deal.

Consider only how much rheumatoid arthritis affected productivity while you were working.

[figure not shown]

CIRCLE A NUMBER

6. During the past seven days, how much did your rheumatoid arthritis problems affect your ability to perform your normal daily activities, other than work at a job?

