#### 4. SAMPLE SIZE AND POWER

Approximately 100 patients diagnosed with RA will be recruited per country. The sample size was calculated by assuming an alpha of 0.05 and a power of 0.80 in a two-sided test, resulting in 52 subjects required to recognize a statistically significant improvement in HAQ DI (-0.21) (11). Given the importance of other secondary endpoints, an improvement of  $9.9 \pm 25$  hours of work time lost requires 58 subjects, assuming an alpha of 0.05 and a power of 0.80 in a two-sided test (12). However, since it is expected that approximately half the study population may no longer be working due to their age, approximately twice this number (100 patients) will be required to achieve the required number of respondents. We have also assumed a drop-out rate of 13% (assuming between 10%-15%).

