#### **5.4 Analysis Plan for Secondary Objectives**

In addition to HAQ DI score, the effect of adalimumab will also be assessed by the secondary outcome measures which are changes to the Short Form 36-Item Health Survey (SF-36) domain scores, EuroQol 5 dimension 3 level (EQ-5D-3L) index, WPAI outcomes, and Patient Treatment Satisfaction Questions at 12 and 24 weeks after the initiation of adalimumab in RA.

- As to the Short Form 36-Item Health Survey (SF-36) domain scores, the Excel Table 4 summarizes the changes in PCS T-score and MCS T-score at 12 and 24 weeks after the initiation of adalimumab; these changes will be summarized as the mean, SD, minimum, maximum, median, 95% confidence interval; and the mean change will be tested with paired t-tests with p-value listed in the table.
- As to the EuroQol 5 dimension 3 level quality of life questionnaire, the Excel Table 5 summarizes the changes in EQ-5D-3L index at 12 and 24 weeks after the initiation of adalimumab; these changes will be summarized as the mean, SD, minimum, maximum, median, 95% confidence interval; and the mean change will be tested with paired t-tests with p-value listed in the table.
- As to the WPAI outcomes, the Excel Table 6 summarizes the changes in percent overall work impairment and percent activity impairment at 12 and 24 weeks after the initiation of adalimumab; these changes will be summarized as the mean, SD, minimum, maximum, median, 95% confidence interval; and the mean change will be tested with paired t-tests with p-value listed in the table.
- Excel Table 7 describes the change in 4 patient satisfaction questions at weeks 12 and 24 after the initiation of adalimumab, in those patients continuing on adalimumab (responder population). These changes will be summarized as number and percentage of each response and compared with Wilcoxon signed rank test shown by p-value1. Satisfaction will also be dichotomized and analyzed over time with Cochran-Armitage test for trends shown by p-value2 in the table.

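### Protocol 9.5 sizes the study with a one-sided test but 9.7.3 makes all tests two-tailed, so the stated 80% power for hours of work time lost is really about 69–71%

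*Protocol*

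**What the plan says.** Protocol 9.5 gives the basis for the enrolment figure: "The sample size was calculated by assuming an alpha of 0.05 and a power of 0.80 in a one-sided test". It prints the normal quantiles 1.645 and 0.842. HAQ DI (mean change -0.21, SD 0.5) needs 36 subjects, and hours of work time lost (9.9, SD 25) needs 40. The 40 is then divided by a 50% employment rate and by 1 minus a 10% drop-out rate to give 89. The abstract repeats the one-sided basis with 36, 40 and 89.

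Protocol 9.7.3 sets the rule for the analysis: "All statistical tests will be two-tailed with a significance level of 0.05". Neither the protocol nor the SAP exempts HAQ DI or WPAI from it.

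The WPAI analyses are of other quantities than hours lost. Protocol 9.7.5 lists "Change in other patient reported outcomes (SF-36 domain scales, EQ-5D Index, WPAI total lost productivity) at weeks 12 and 24", to be tested with paired t-tests. SAP 5.4 says that "the Excel Table 6 summarizes the changes in percent overall work impairment and percent activity impairment at 12 and 24 weeks", again with paired t-tests.

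SAP section 4 (V0.2, 2 January 2018, written for three countries) sizes each country with a two-sided test, from the same HAQ DI change of -0.21 and the same 9.9 ± 25 hours. It gives 52 for HAQ DI and 58 for hours lost, then says that because about half the patients may not be working, "approximately twice this number (100 patients) will be required to achieve the required number of respondents". It assumes 13% drop-out.

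**The concern.** The power in 9.5 belongs to a one-sided 5% test, and the plan does not use one. The mismatch affects the variable that fixes enrolment: HAQ DI alone would need far fewer than 89 patients, so the figure rests on hours lost and on the 80% attached to it. A reader who meets a non-significant work-productivity result would judge it against a power that the prescribed two-tailed rule does not deliver.

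The SAP adds a second problem. It justifies the Korean sample on another basis (two-sided, 100 patients, 13% drop-out) from that in the protocol (one-sided, 89 patients, 10% drop-out). A study report could cite either.

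**Working it through.** **Inputs.** From protocol 9.5: alpha 0.05, power 0.80, HAQ DI -0.21 with SD 0.5, hours lost 9.9 with SD 25, 50% employed, 10% drop-out. From protocol 9.7.3: two-tailed tests at 0.05. From SAP section 4: 52, 58, 100 per country, 13% drop-out.

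**Formulas** for a single-group paired change, with d = mean/SD:
- n = ((z_alpha + z_power)/d)², rounded up
- power = Φ(d√n − z_alpha), checked against the noncentral t distribution of the paired t-test
- d = 0.21/0.5 = 0.42 for HAQ DI; d = 9.9/25 = 0.396 for hours lost

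**Step 1: reproduce 9.5 (one-sided, z = 1.645).**
- HAQ DI: (2.487/0.42)² ≈ 35.05, so 36, as stated.
- Hours lost: (2.487/0.396)² ≈ 39.43, so 40, as stated.
- Enrolment: 40/0.5/0.9 = 88.9, so 89, as stated.

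The arithmetic is correct for a one-sided test.

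**Step 2: apply the two-tailed rule (z = 1.960) to the 89 patients.**
- Employed completers: 89 × 0.9 × 0.5 = 40.05, about 40.
- Power for hours lost: 0.396 × √40 = 2.5045; Φ(2.5045 − 1.960) = 70.7%. The exact paired t-test gives 68.5%.
- Smallest mean change detectable with 80% power: (1.960 + 0.842) × 25/√40 = 11.1 hours (11.4 by t), against the 9.9 assumed.

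**Step 3: what 80% two-sided power would need.**

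| | Normal | Paired t |
|---|---|---|
| Employed completers, hours lost | 50.05, so 51 | 53 |
| Enrolled (÷ 0.5 ÷ 0.9) | 113.3, so 114 | 117.8, so 118 |
| Or employment rate at 89 enrolled (÷ 80.1 completers) | 64% | 66% |
| Completers, HAQ DI | 44.49, so 45 | 47 |

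**Step 4: primary endpoint.** 89 × 0.9 is about 80 completers. Two-sided power for HAQ DI is Φ(0.42 × √80 − 1.960) = 96.4% (96.0% by t).

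**Step 5: the SAP's text.** Twice 58 is 116, not 100. With 100 enrolled, 100 × 0.5 × 0.87 = 43.5 employed completers. Two-sided power at 43 or 44 is 73.8% or 74.8% (71.8% or 72.8% by t), so the SAP's own two-sided 80% is not met either. The 52 and 58 match 44.49/0.87 = 51.1 and 50.05/0.87 = 57.5 rounded up, so drop-out is probably already inside them. That is an inference; the SAP does not say so.

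**Step 6: how far the figure reaches.** The 69–71% applies to hours lost only. The documents give no mean change or SD for total lost productivity, percent overall work impairment or percent activity impairment. The last is not confined to employed patients either: Appendix G tells those not in paid work, "If your response is 3-6, skip to question 6", and question 6 is the activity item. The 9.9 hours may also not be on the questionnaire's time scale. Protocol 9.2.4.7 says "The WPAI is a patient-reported questionnaire to measure work and activity impairment during the past seven days", and nothing shows that the assumed 9.9 ± 25 refers to seven days.

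**The case against.** The strongest reply is that no section plans a test of change in hours lost. The WPAI tests are on percentage scores, so 69–71% illustrates the sizing assumption and is not a demonstrated loss of power in a listed analysis. This is right and limits the point. It does not rescue 9.5, which claims 80% for hours lost and derives 89 from it; under 9.7.3 that claim is wrong as written.

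A second reply is that little follows in practice. The study is single-arm and observational, the primary endpoint is well powered, and the planned tests are already two-sided, so type I error is untouched. All of this stands, and it is why the point calls for a correction and does not threaten the primary conclusion.

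Third, timing. Data collection was due to end on 28 February 2018 and the visible approval dates of Amendment 01 run from 3 March to 12 April 2018. Restating 9.5 would be a further amendment after the planned end of data collection. That is a reason to date the correction openly and not to seek more patients. It is no reason to leave the 80% in place.

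Fourth, the SAP says approximately twice, and if 58 already includes drop-out, doubling the roughly 50 completers behind it gives about 100. But on that reading 58 is the number of employed patients to enrol, so total enrolment is 58/0.5 = 116; stopping at 100 leaves drop-out unallowed for.

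Finally, 52 gives 79.996% power by the paired t-test, so 53 reflects strict rounding. The difference is immaterial.

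**Conclusion.** The concern holds. Protocol 9.5 and 9.7.3 disagree on sidedness. For the variable that sets enrolment, the prescribed two-tailed test has about 69–71% power at 40 employed completers, against 80% stated. The result rests on the protocol's own assumptions: 9.9 hours with SD 25, 50% employment and 10% drop-out. HAQ DI keeps about 96% two-sided power and is unaffected. The power for the WPAI scores that will be tested cannot be stated from the documents. SAP section 4 conflicts with the protocol on sidedness, enrolment and drop-out, and its 100 does not follow from its own 58. This should be fixed; confidence is high.

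**What to change.** Keep 89 patients and the two-tailed tests. Restate protocol 9.5, the abstract and SAP section 4 on one two-sided basis, for example:

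> All tests are two-sided at 0.05. For HAQ DI (mean change -0.21, SD 0.5), 80% power needs 45 completers (47 by paired t-test); about 80 completers give about 96%. For hours of work time lost (9.9, SD 25), about 40 employed completers give about 69% power by paired t-test (71% by normal approximation), and the smallest mean change detectable with 80% power is about 11.4 hours (11.1 normal). No power is claimed for WPAI total lost productivity, percent overall work impairment or percent activity impairment.

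Withdraw the 80% claim for WPAI and, for Korea, the SAP's text with 52, 58, 100 and 13%. SAP 3.2 repeats 100 per country and should be aligned. Date the change, so that it reads as a correction and not as the original design basis.

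Optionally, change in hours missed (WPAI question 2) could be added to Table 6, but only if the sponsor confirms that the 9.9 ± 25 hours use the same seven-day recall. That would be a new analysis and is not needed for the correction.

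The correction itself costs wording only, with no extra patients and no change of test. The price is candour: the stated power for hours lost falls from 80% to about 69–71%, and no power is given for the WPAI scores actually tested.

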17.0 Discontinuation or Drop-out

Patients' participation in the study is completely voluntary, and they are allowed to withdraw or discontinue from the study. The following three situations will be counted as study drop-out:

- 1) Patient is switched off Adalimumab
- 2) Patient is not willing to continue participation in the study
- 3) Patient disappears and cannot be contacted anymore

For the first two situations, the Early Termination Form (Appendix K) will be provided for the patients and their physicians to fill in.

Patients not completing questionnaires will not be classified as drop-out. For example, if a patient missed Week 12 questionnaires for some reason, he/she can still fill in Week 24 questionnaires.

Once a subject is dropped out from the study, no further information for that subject will be collected. However, the reason for drop-out will be collected and, if the reason for treatment discontinuation is due to an adverse event, the event will be reported as follows :

- SAE : reported to Abbvie within 24 hours of physician awareness

- Non-serious AE : reported to Abbvie within 24 hours of PMOS physician awareness.

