### **Scores**

Multiply scores by 100 to express in percentages.

- Percent work time missed due to problem

$$Q2 / (Q2+Q4)$$

- Percent impairment while working due to problem

$$Q5 / 10$$

- Percent overall work impairment due to problem

$$Q2/(Q2+Q4)+[(1-Q2/(Q2+Q4) \times (Q5/10)]$$

- Percent activity impairment due to problem

$$Q6 / 10$$

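### The WPAI calculation that sets N = 89 uses hours of work time lost, which no named change-from-baseline test analyses; the power of the WPAI tests that are planned is not stated.

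*Protocol*

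**What the plan says.** Protocol 9.5 sizes the study on two measures: "The sample size was calculated by assuming an alpha of 0.05 and a power of 0.80 in a one-sided test". For the primary endpoint it assumes a mean change in HAQ-DI "of -0.21 and a standard deviation (SD) of 0.5, according to the formula, 36 subjects are required". It then turns to the WPAI as an important secondary endpoint: "an improvement of 9.9 ± 25 hours of work time lost (mean=9.9, SD=25) requires 40 subjects". The 40 are divided by 50% employment and by 0.9 for drop-out to reach 89. SAP 4 sizes on the same 9.9 ± 25 hours, although it still gives 58 subjects and about 100 patients per country under a two-sided test.

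The planned tests use other measures. Protocol 9.7.5 applies a paired t-test to WPAI total lost productivity at Weeks 12 and 24. SAP 2.2 repeats that term, and neither document defines it. SAP 5.4 says that Table 6 "summarizes the changes in percent overall work impairment and percent activity impairment at 12 and 24 weeks", with 95% CIs and paired t-tests.

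Hours missed are collected. Item Q2 of the form in Protocol Appendix G asks: "During the past seven days, how many hours did you miss from work because of problems associated with your rheumatoid arthritis". The SAP scoring section (3.5.1) also defines "Percent work time missed due to problem" as Q2/(Q2+Q4). SAP 5.4 does not name either of them as a row of Table 6.

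**The concern.** The outcome that fixes the enrolment target should be one that the analysis plan names and tests. Here it is not, and the WPAI scores that are tested lie on a different scale with no planning assumptions behind them. Protocol 7.0 says that the WPAI results will interest payers. A reader who sees 80% power in the sample-size section is likely to attach it to Table 6, where no power was calculated.

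There is a second cost. If no work-time score is named beforehand, the choice among several WPAI scores stays open until results are seen.

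**Working it through.** **Inputs.** Protocol 9.5: alpha 0.05 one-sided, power 0.80, z values 1.645 and 0.842; HAQ-DI change -0.21, SD 0.5; hours 9.9, SD 25; 50% employed; 10% drop-out. Protocol 9.7.3: all tests two-tailed at 0.05.

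**1. The plan's own figures**, with n = (SD × (z(1-α) + z(1-β)) / Δ)²:

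- Hours: (25 × 2.487 / 9.9)² = 39.4, so 40.
- HAQ-DI: (0.5 × 2.487 / 0.21)² = 35.1, so 36.
- Enrolment: 40 / 0.5 / 0.9 = 88.9, so 89.

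All three reproduce. HAQ-DI alone would need 36 / 0.9 = 40 enrolled, so 89 - 40 = 49 of the planned patients are there because of the hours calculation.

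**2. Is the sized measure tested?**

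| Measure | Sized in Protocol 9.5 | Scored in SAP 3.5.1 | Named change test |
|---|---|---|---|
| Hours missed (Q2) | Yes | No (input item only) | None |
| Percent work time missed, Q2/(Q2+Q4) | No | Yes | None |
| Percent overall work impairment | No | Yes | SAP 5.4, Table 6 |
| Percent activity impairment, Q6/10 | No | Yes | SAP 5.4, Table 6 |
| WPAI total lost productivity | No | Not defined | Protocol 9.7.5, SAP 2.2 |

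Activity impairment contains no work time. Overall work impairment contains Q2/(Q2+Q4) but combines it with impairment while at work (Q5). An effect and SD in hours therefore carry over to neither score.

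**3. Power for hours under the planned test.** The standardized change is 9.9/25 = 0.396, with n = 40:

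- One-sided 0.05: 80.5% (normal approximation).
- Two-sided 0.05: 70.7% (normal approximation), 68.5% (noncentral t).

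Two-sided 80% power would need 51 employed completers (53 by noncentral t). That is 51 / 0.45 = 113.3, so 114 enrolled (53 / 0.45 = 117.8, so 118).

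**4. Overall work impairment.** The documents give no effect or SD, so only a detectable change can be stated. With 40 employed patients who have both forms, a two-sided 0.05 paired t-test has 80% power for 0.454 SD of change (noncentral t; 0.443 by normal approximation). For an assumed SD of change of 20, 25 or 30 points, 0.454 × SD gives 9.1, 11.4 or 13.6 points. Power for an assumed standardized change (noncentral t) is:

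| Standardized change | Power at n = 40 |
|---|---|
| 0.2 | 23% |
| 0.3 | 46% |
| 0.5 | 87% |
| 0.6 | 96% |

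**5. Primary endpoint.** 89 × 0.9 = 80.1, so about 80 completers. At -0.21, SD 0.5, two-sided power is 96.4% (normal approximation), 96.0% (noncentral t).

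**The case against.** The best defence is that work time is not absent from the plan. Protocol 9.3 lists change in WPAI without narrowing it to a score. The opening of SAP 5.4 and the association models in SAP 5.5 speak of WPAI outcomes in general. Percent overall work impairment contains the work-time-missed fraction. The table shells are a separate file that cannot be checked here, and 95% CIs for the tested WPAI changes are already planned.

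This limits the claim to tests that are named. It does not remove the gap: SAP 5.4 goes on to name the two scores in Table 6, SAP 5.5 concerns regression on DAS28 rather than change from baseline, and a composite that includes work time missed is not the measure that was sized.

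A reader might infer more than the documents support:

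- *That the 80% power belongs to no reported result.* Protocol 9.5 applies the same 0.80 to HAQ-DI, which is the primary endpoint and is tested.
- *That the study cannot report the work outcome it was sized for.* Item Q2 is collected and percent work time missed is already defined; what is missing is a named analysis.
- *That an SD of 25 hours is near the limit for a seven-day item.* On an assumed 40-hour week, a change bounded at ±40 with mean -9.9 can have an SD up to √(49.9 × 30.1) = 38.8 hours, so 25 is about 64% of the maximum. The documents do not state the period behind 9.9 ± 25 hours, so all that can be asked is that it be given.

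**Conclusion.** The point holds for the WPAI only. The calculation that fixes N = 89 rests on a measure with no named change-from-baseline test, and the WPAI scores that are tested have no stated effect, SD or power. Under the planned two-sided test the hours assumption carries about 69% power (71% by normal approximation), not 80%. Overall work impairment has 80% power only for a change of about 0.45 SD.

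These figures take the protocol's 40 employed completers as given. The values in points rest on an assumed SD of 20 to 30. The primary HAQ-DI conclusion is not affected. This should be corrected before analysis, because the justification for N and the work-productivity analysis do not match.

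**What to change.** 1. **SAP 5.4 and Table 6.** Add change in hours of work missed (Q2), with percent work time missed, Q2/(Q2+Q4), as a supporting row, at Weeks 12 and 24 in employed patients. Report the mean, 95% CI and paired t-test, labelled as secondary. Say which SAP score WPAI total lost productivity means.
2. **Protocol 9.5 and SAP 4.** Say that 9.9 ± 25 hours applies only to the hours row, and give its reference period. Restate its power under the two-sided 0.05 test as about 69% with 40 employed completers. Bring the 58 subjects and 100 patients in SAP 4 into line at the same time.
3. **Same sections.** State that no power was calculated for percent overall work impairment, and give the detectable change: about 0.45 SD with 40 employed patients who have both forms, with the range in points and its assumed SDs.

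No new data or patients are needed. The cost is four more secondary tests (two scores at two visits), which is why hours should be named as the main row and the percent score as supporting, and a less favourable power statement.
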